16.1 Informed Consent Process

Informed consent is a process where information is presented to enable persons to voluntarily decide whether or not to participate as a research subject. It is an

ongoing conversation between the human research subject and the researchers which begins before consent is given and continues until the end of the subject's involvement in the research. Discussions about the research will provide essential information about the study and include: purpose, duration, experimental procedures, alternatives, risks and benefits. Subjects will be given the opportunity to ask questions and have them answered.

The subjects will sign the informed consent document prior to undergoing any research procedures. The subjects may withdraw consent at any time throughout the course of the trial. A copy of the informed consent document will be given to the subjects for their records. The researcher will document the signing of the consent form in the subject's medical record. The rights and welfare of the subjects will be protected by emphasizing to them that the quality of their medical care will not be adversely affected if they decline to participate in this study.

16.2 Subject Confidentiality

All records will be kept confidential to the extent provided by federal, state and local law. The study monitors and other authorized individuals may inspect all documents and records required to be maintained by the Investigator, including but not limited to, medical records. Records will be kept locked and data will be coded. Any personally identifiable information maintained for this study will be kept on restricted-access computers and networks. Personally identifiable information will only be shared with individuals authorized to receive it under this protocol. Individuals not authorized to receive personally identifiable information will be provided with coded information only, as needed. Clinical information will not be released without written permission of the subject, except as necessary for monitoring by the IRB, the NIAID, the Office of Human Research Protections, or GSK.

To further protect the privacy of study subjects, a Certificate of Confidentiality has been issued by the NIH. This certificate protects identifiable research information from forced disclosure. It allows the investigator and others who have access to research records to refuse to disclose identifying information on research participation in any civil, criminal, administrative, legislative, or other proceeding, whether at the federal, state, or local level. By protecting researchers and institutions from being compelled to disclose information that would identify research subjects, Certificates of Confidentiality help achieve the research objectives and promote participation in studies by helping assure confidentiality and privacy to subjects.

17. Data Handling and Record Keeping

17.1 Data Capture and Management

Study data will be maintained in CRIMSON, and collected directly from subjects during study visits and telephone or virtual contacts, or will be abstracted from subjects' medical records. Source documents include all recordings of observations or notations of clinical activities and all reports and records necessary to confirm the data abstracted for this study. Data entry into CRIMSON will be performed by authorized individuals. The Investigator is responsible for assuring that the data collected are complete, accurate, and recorded in a timely manner.

17.2 Record Retention

Study records will be maintained by the principal investigator in accordance with regulatory and institutional requirements, ICH GCP guidelines, and the NIH Intramural Records Retention Schedule. All stored records will be kept confidential to the extent required by federal, state, and local law. No records will be destroyed without the written consent of the principal investigator.

Appendix B: Schedule of Procedures/Evaluations

Table 1. Schedule of Procedures/Evaluations for the Primary Study Phase.

Evaluations	Enrollment	Home Labs§	Baseline (Peak ANC)	Home Labs§	Peak AEC	Home Labs§	Study Drug 700mg/ AEC Nadir	Home Labs§	Predict ed ANC Peak	Home Labs§	Study Drug 700mg	Primary Assess-ments*	U V
Visit Number	1		2		3		4		5		6	7	8
Day (assuming 4-week cycle)¶	Day -30 to -15		Day 0		Day 7		Day 15		Will vary		Day 43	Day 71	Day 99
Window (days)					±3		±3		-		±5	±5	±7
Consent and clinical assessments													
Informed consent	X												
Complete medical history and physical examination	X		X										
Targeted medical history and physical examination				X		X		X		X		X	
Limb measurements	X		X		X		X		X		X		X
Vital signs including weight	X		X		X		X		X		X		X
Photography with/without infrared thermography	X		X					X		X		X	
Symptom log and PROs#	X		X		X		X		X		X		X
Optional bone marrow biopsy and aspiration	X†		X†									X‡	
Optional skin punch biopsy	X†		X†		X†		X†						

Study drug administration		Clinical and safety laboratory testing										Research laboratory studies			
Mepolizumab															
CBC with differential	X	X	X	X	X	X	X	X	X	X	X	X	X	X	X
Acute care panel	X	X										X	X	X	X
Hepatic panel	X	X										X	X	X	X
Mineral panel	X	X										X	X	X	X
LDH, CPK	X											X	X	X	X
C-reactive protein	X	X										X	X	X	X
Urinalysis	X	X										X	X	X	X
Serum tryptase	X	X										X	X	X	X
Serum aldolase	X	X										X	X	X	X
Serum immunoglobulins	X	X										X	X	X	X
Serum IgE levels	X	X										X	X	X	X
Urine pregnancy test*		(X)										(X)	(X)	(X)	(X)
Research laboratory studies															
Eosinophil and PBMC purification from whole blood and storage	X											X			X
Urine for eosinophil granule protein and mediator levels	X	X										X	X	X	X
Whole blood flow for TBNK cell subsets and RNAseq	X											X	X	X	X
Serum or plasma for eosinophil granule protein and mediator levels	X											X	X	X	X

Study assessments															
AE assessments		X		X		X		X		X		X		X	

Key: AE- adverse event; AEC- absolute eosinophil count; ANC- absolute neutrophil count; CBC- complete blood count; CPK- creatine kinase; IgE- immunoglobulin E; LDH- lactate dehydrogenase; PBMC- peripheral blood mononuclear cell; PROs- patient-reported outcome measures; TBNK- T, B, and natural killer cell; UV- unscheduled visits; ¹ Study visits may be rescheduled or study procedures may be waived or modified to be performed remotely due to travel limitations or safety concerns during the coronavirus disease 2019 pandemic (as described in protocol section 6); ² All subjects will complete Visit 8. Subjects who experienced benefit from mepolizumab administration will continue in the de-escalation phase (which begins with additional procedures at Visit 8—see Table 2 below); for subjects who do not continue in the de-escalation phase, Visit 8 will be the final study visit. ³ The exact timing of Visit 1 through Visit 5 may vary from this schedule based on subject cycle times. Visits 2 and 3 may be combined if neutrophils and eosinophils peak <1 week apart. Every effort will be made to schedule Visit 5 in advance of Visit 6; in the event that Visit 5 occurs within 1 day of Visit 6, only collection of whole blood for storage will be performed for Visit 5. Visits 6, 7, and 8 will be scheduled monthly based on the timing of Visit 4. ⁴ Urine pregnancy test prior to administration of mepolizumab in women of child-bearing potential; ⁵ Performed electronically via REDCap. Symptom logs to be performed daily; PROs daily and monthly, not only at study visits; daily symptom logs and measures will be discontinued after Visit 7, and monthly questionnaires will be continued through Visit 8; ⁶ Home labs will be done 2-3X/week, depending on subject cycle times (2X/week in some cases or after peak is obtained); ⁷ Optional. Bone marrow will be requested to be performed only once at Visit 1 or 2, if a sample is not available from another NIH protocol. Skin punch biopsy will be requested to be performed only once on Visits 1, 2, or 3; ⁸ May be requested once at any time while on study drug if a pre-treatment sample was collected/available.

Table 2. Schedule of Procedures/Evaluations for the De-escalation Phase.

Evaluations	Study Drug 500 mg	Study Drug 500 mg	Study Drug 500 mg	Study Drug 300 mg	End of De-escalation	UV			
Visit Number	8	9	10	11	12	13	14		
Day (assuming 4-week cycle)	Day 99	Day 127	Day 155	Day 183	Day 211	Day 239	Day 267		
Window (days)	±7	±7	±7	±7	±7	±7	±7		
Clinical assessments and laboratory evaluations									
Targeted medical history and physical examination	X	X	X	X	X	X	X	X	X
Limb measurements[^]	X	X	X	X	X	X	X	X	X
Vital signs including weight[^]	X	X	X	X	X	X	X	X	X
Symptom log and PROs[#]	X	X	X	X	X	X	X	X	X
Autoinjector training (for remote subjects)	X								
Mepolizumab	X	X	X	X	X	X			
CBC with differential		X	X	X	X	X	X	X	X
Hepatic panel			X				X		
Mineral panel			X				X		
LDH, CPK				X				X	
C-reactive protein				X				X	X
Urinalysis				X				X	X

Serum tryptase		X				X	X
Serum aldolase		X				X	X
Serum immunoglobulins	X					X	X
Serum IgE levels	X					X	X
Urine pregnancy test*	(X)						
Research laboratory studies							
Eosinophil and PBMC purification from whole blood and storage		X				X	
Urine for eosinophil granule protein and mediator levels	X	X				X	
Whole blood flow for TBNK cell subsets and RNAseq		X				X	
Serum or plasma for eosinophil granule protein and mediator levels	X	X				X	
Study assessments							
AE assessments	X	X	X	X	X	X	X

Key: AE- adverse event; CBC- complete blood count; CPK- creatine kinase; IgE- immunoglobulin E; LDH- lactate dehydrogenase; PBMC- peripheral blood mononuclear cell; PROs- patient-reported outcome measures; TBNK- T, B, and natural killer cell; UV- unscheduled visits; ¹¹ Study visits may be rescheduled or study procedures may be waived or modified to be performed remotely due to travel limitations or safety concerns during the coronavirus disease 2019 pandemic (as described in protocol section [6](#)); ¹² Some vital signs or assessments may not be possible if performed virtually. Visit 8 will begin after completion of procedures listed at Visit 8 in [Table 2](#). Visits 9 to 14 will be scheduled 28 days (\pm 7 days) from the prior visit. * Urine pregnancy test prior to administration of mepolizumab in women of child-bearing potential (not performed at remote visits); [#] Performed electronically via REDCap. A weekly symptom log will be completed through Visit 14; PROs will be done weekly and monthly through Visit 14.

Appendix C: Blood Volumes for Specimen Collection

Table 3. Blood Volumes for Collection in the Primary Study Phase.

Evaluations	Enrollment V1	Home Labs ²	Baseline V2	Home Labs ²	Peak AEC V3	Home Labs ²	Study Drug/ AEC Nadir V4	Predicted ANC Peak V5	Home Labs ²	Study Drug V6	Study Drug V7	V8 (± Study Drug)
CBC with differential	Light Lavender, EDTA	3	3	3	3	3		3		3	3	3
Acute care, hepatic, and mineral panels	Green-Yellow rim	4	4	4	4	4		4		4	4	4
C-reactive protein	Green-Yellow rim	X	X	X	X	X		X		X	X	X
Immunoglobulins (quantitative)	Green-Yellow rim	X	X	X	X	X		X		X	X	X
LDH, CPK	Green-Yellow rim	X		X	X	X		X		X	X	X
Aldolase, serum	Red-Yellow SST	4	4	4	4	4		4		4	4	4
Tryptase, serum	Red-Yellow SST	X	X	X	X	X		X		X	X	X
IgE	Red-Yellow SST	X	X	X	X	X		X		X	X	X
CBC with differential	Light Lavender, EDTA	12	12	12	12	12		12				12
Whole blood for cells and plasma	Light Lavender, EDTA	40	40	40	40	40		40				40
Serum for storage	Red-Yellow SST	8	8	8	8	8		8		8	8	8
TBNK-eos	Light Lavender, EDTA	3	3	3	3	3		3		3	3	3

RNA PAX	PAXgene	2.5	2.5	2.5	2.5	2.5	2.5	2.5	2.5	2.5	2.5	2.5
Daily or Interval Volume (mL)	64.5	12	64.5	12	64.5	12	64.5	12	64.5	12	19	11
Cumulative Volume (mL)	64.5	76.5	141	153	217.5	229.5	294	306	370.5	382.5	401.5	412.5

Abbreviations: AEC- absolute eosinophil count; ANC- absolute neutrophil count; CBC- complete blood count; CPK- creatine kinase; EDTA- ethylenediaminetetraacetic acid; IgE- immunoglobulin E; LDH- lactate dehydrogenase; TBNK- T, B, and natural kill cell; V- visit.

¹ Specific timing of visits is provided in the Schedule of Evaluations ([Appendix B](#)) and Study Schematic (section [3.2](#)). Per NIH MEC Policy M95-9, maximum blood volumes drawn for research purposes for an adult subject (aged 18 years or older) may not exceed: 10.5 mL/kg or 550 mL, whichever is smaller, over any 8-week period. This table reflects a model 4-week EAE cycle time with Day-15 enrollment, which would result in the highest possible blood volumes per time period. Blood volumes may be adjusted as needed for in-person visits that are changed to remote visits during the coronavirus disease 2019 pandemic.

² Home lab blood volumes reflect total volume over interval. Home lab collections may be performed 2 times per week in subjects with 4-week or shorter cycle times or after peak is obtained. For subjects with longer cycle times, home labs will be performed up to 3 times per week without exceeding the NIH CC blood volume limit.

³ Day 0 evaluations are the baseline for subsequent safety assessments.

Table 4. Blood Volumes for Collection in the Dose De-escalation Phase.

Evaluations (De-escalation phase)	Study Drug V9	Study Drug V10	Study Drug V11	Study Drug V12	Study Drug V13	End of De-escalation V14
CBC with differential	Light Lavender, EDTA	3	3	3	3	3
Acute care, hepatic, and mineral panels	Green-Yellow rim		4			4
C-reactive protein	Green-Yellow rim		X			X
Immunoglobulins (quantitative)	Green-Yellow rim		X			X
LDH, CPK	Green-Yellow rim		X			X
Aldolase, serum	Red-Yellow SST		4			4

Tryptase, serum	Red-Yellow SST	X			X
IgE	Red-Yellow SST	X			X
Whole blood for cells and plasma	Light Lavender, EDTA	40			40
Serum for storage	Red-Yellow SST	8	8		8
TBNK-eos	Light Lavender, EDTA		3		3
RNA PAX	PAXgene		2.5		2.5
Daily or Interval Volume (mL)	22	64.5	3	3	64.5
Cumulative Volume (mL)	499	563.5	566.5	569.5	572.5
					637

[figure not shown]
[figure not shown]
[figure not shown]
[figure not shown]
Abbreviations: CBC- complete blood count; CPK- creatine kinase; EDTA- ethylenediaminetetraacetic acid; IgE- immunoglobulin E; LDH- lactate dehydrogenase; TBNK- T, B, and natural kill cell; V- visit.

[figure not shown]
[figure not shown]
¹ Specific timing of visits is provided in the Schedule of Evaluations ([Appendix B](#)) and Study Schematic (section [3.2](#)). Per NIH MEC Policy M95-9, maximum blood volumes drawn for research purposes for an adult subject (aged 18 years or older) may not exceed: 10.5 mL/kg or 550 mL, whichever is smaller, over any 8-week period. This table reflects a model 4-week EAE cycle time with Day -15 enrollment, which would result in the highest possible blood volumes per time period. Blood volumes may be adjusted as needed for in-person visits that are changed to remote visits during the coronavirus disease 2019 pandemic.

² Home lab blood volumes reflect total volume over interval. Home lab collections may be performed 2 times per week in subjects with 4-week or shorter cycle times or after peak is obtained. For subjects with longer cycle times, home labs will be performed up to 3 times per week without exceeding the NIH CC blood volume limit.

³ Day 0 evaluations are the baseline for subsequent safety assessments.

Appendix D: Cycle Length Determination for 3 Patients

Appendix E: Patient Symptom Log (Daily)

The following information will be captured on an electronic version of this log through REDCap.

Name:

Instructions: Record oral temperature and write "C" for degrees Celsius or "F" for degrees Fahrenheit. Take temperature and weight around the same time each day, preferably morning.

Rate the severity of **general symptoms** experienced due to your EAE each day. If there were no symptoms on one day, check the "No Symptoms" box and leave blank all listed symptoms.

Record all **medications** taken for any of the above symptoms for each day (name, dose, number of times taken, how often taken, and reason; for example, "Ibuprofen, 200 mg, 2 tabs 4 times today for headache"). If there were no medications on a particular day, the "None" box should be checked.

Date (mm/dd)	—	—	—	—	—	—	—	—	—
Temperature (write F or °C)	—	—	—	—	—	—	—	—	—
Weight (write lbs or kg)	—	—	—	—	—	—	—	—	—
GENERAL SYMPTOMS									
NO SYMPTOMS If you have any of the symptoms below, then rate their severity from 1 to 4: 1 – mild; 2 – moderate; 3 – severe; 4 – severe and leads to doctor/ER visit or hospitalization									
Fever	—	—	—	—	—	—	—	—	—
Muscle and body aches	—	—	—	—	—	—	—	—	—
Swelling	—	—	—	—	—	—	—	—	—
Swollen lymph nodes	—	—	—	—	—	—	—	—	—
Hives	—	—	—	—	—	—	—	—	—
Pain, redness, swelling, itching, or burning at injection site (please specify)	—	—	—	—	—	—	—	—	—
Rash	—	—	—	—	—	—	—	—	—
Fatigue	—	—	—	—	—	—	—	—	—
Headache	—	—	—	—	—	—	—	—	—
Other symptoms (please describe)	—	—	—	—	—	—	—	—	—
MEDICATIONS OR OTHER EVENT									
Were you evaluated by a health professional?	NONE								
List all medications taken for any of the above symptoms, or any other event. Also list any changes in medication.	—	—	—	—	—	—	—	—	—

If you experience new symptoms or have questions, contact [name] at [contact], [contact]; or [name] at [contact], [contact]. For after hours or weekend emergencies, call the NIH page operator at [contact] to page [name].

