LDH	Lactate Dehydrogenase
LPD	Laboratory of Parasitic Diseases
N	Number (typically refers to number of subjects/sample size)
NIAID	National Institute of Allergy and Infectious Diseases
NIH	National Institutes of Health
OHSRP	Office of Human Subjects Research Protections
PBMC	Peripheral Blood Mononuclear Cell
RNAseq	RNA sequencing
SAE	Serious Adverse Event
SC	Subcutaneous
TBNK	T-, B-, and Natural Killer–Cell Analysis
UP	Unanticipated Problem
U.S.	United States

Protocol Summary

Full Title:	Pilot Study of Mepolizumab in Episodic Angioedema with Eosinophilia
Short Title:	Mepolizumab in EAE
Sample Size:	N = 12
Accrual Ceiling:	15
Study Population:	Adult subjects with confirmed episodic angioedema with eosinophilia (EAE)
Accrual Period:	2 years
Study Design:	
This will be an open-label pilot study. Following completion of eligibility assessments, subjects with confirmed EAE will enter a run-in period, during which the periodicity of their cycle will be assessed (if not known) and the optimal timing of the baseline visit will be determined. During this time, subjects will begin daily and monthly patient-reported outcome measures; the daily measures will be continued for about 3 months (through the third mepolizumab dose), and the monthly measures will be continued through the end of the primary study phase. Also, subjects will begin visiting a local lab 2-3X/week for collection of blood for complete blood count (CBC) with differential and serum and urine to be mailed to NIH for research; local lab visits will continue between study visits through the second mepolizumab administration. Once cycling and periodicity is confirmed, the baseline visit will be scheduled at the predicted neutrophil peak. Baseline assessments will include history and physical examination, routine laboratory testing, and whole blood flow cytometric analysis. Subjects will again be evaluated and have bloodwork during their predicted eosinophil peak (may be concurrent with baseline if peak eosinophils and neutrophils occur <1 week apart) and at the next predicted eosinophil nadir; at the nadir visit, they will receive their first administration of mepolizumab (700 mg via intravenous [IV] infusion). Subjects will return to the NIH at the predicted neutrophil peak for clinical evaluation and whole blood flow cytometry.

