3.3 Study Endpoints

3.3.1 Primary Endpoint

Reduction in the number and severity of clinical symptoms associated with EAE after 3 doses of mepolizumab (as compared to symptoms logged in the approximately monthly cycle preceding initiation of mepolizumab).

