7.1.3 Symptom Logs and Patient-reported Outcomes

Patients will fill out a daily log capturing symptoms, weight, and temperature (Appendix E: Patient Symptom Log), and fill out validated patient-reported outcome measures for angioedema (daily) and quality of life (monthly; questionnaires provided as [Appendix G](#)). These logs and measures will be completed electronically using REDCap. Subjects will also be encouraged to notify the investigators of any new signs or symptoms that develop between study visits. The daily logs and measures will be completed through the end of study endpoint assessments (Visit 8). For subjects in the de-escalation phase, after Visit 8 until study completion, weekly angioedema and monthly quality of life questionnaires will be continued, and weekly symptoms logs ([Appendix F](#)) will be completed.

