8.1 Potential Risks

8.1.1 Mepolizumab

The risks of mepolizumab and AE profile have been well described in several prior studies of mepolizumab in asthma, eosinophilic granulomatosis with polyangiitis, and HES. ARs with a $\geq 5\%$ incidence include: headache, injection site reactions (pain, erythema, swelling, itching, burning), back pain, and fatigue. Mepolizumab 100 mg and 300 mg have been approved for SC use. The package insert lists the following risks of mepolizumab use: hypersensitivity reactions including anaphylaxis, angioedema, bronchospasm, hypotension, urticaria, and rash; and herpes zoster infection (12). Other noted findings in studies of mepolizumab include the development of anti-drug antibodies; however, neutralizing antibodies were only identified in 1 of 260 patients with severe asthma receiving mepolizumab 100 mg. Such antibodies are not considered to affect the course of treatment. Additionally, there are unknown risks to the fetus in the case of pregnancy or nursing infants (see section 4.3).

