15.1 Study Hypotheses, Endpoint and Sample Size Justification

This is a pilot study designed as proof of principle, and the small sample size is dictated both by our ability to recruit sufficient numbers of patients in this rare disease and the complexity of the study design.

First, based on the fact that there are n=12 subjects already in the natural history protocol, we expect to be able to get n=5 subjects to participate in this study.

For the primary endpoint of change in maximum daily AE score (DAES), we use a quasi-Poisson model to estimate the average percent reduction after treatment compared to pre-treatment. This model accounts for within-person correlation of

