Appendix F: Patient Symptom Log (Weekly)

Pilot Study of Mepolizumab in Episodic Angioedema with Eosinophilia
PARTICIPANT WEEKLY SYMPTOM LOG

Name:

Instructions: Record symptoms you have experienced in the past week due to your EAE.

For any other symptoms attributed to your EAE please indicate the number of days you experienced the symptoms (zero if didn't experience) or number of days experienced and how severe the symptoms were at their worst. **1 – mild; 2 – moderate; 3 – severe; 4 – severe and leads to doctor/ER visit or hospitalization.**

No EAE symptoms in the prior week

Fever

	Frequency (days)							Severity					
0	1	2	3	4	5	6	7	1	2	3	4		

Fatigue

	Frequency (days)							Severity					
0	1	2	3	4	5	6	7	1	2	3	4		

Headache

	Frequency (days)							Severity					
0	1	2	3	4	5	6	7	1	2	3	4		

Other symptoms (please describe)

	Frequency (days)							Severity					
0	1	2	3	4	5	6	7	1	2	3	4		

Swollen lymph nodes

	Frequency (days)							Severity					
0	1	2	3	4	5	6	7	1	2	3	4		

Hives

	Frequency (days)							Severity					
0	1	2	3	4	5	6	7	1	2	3	4		

Rash

	Frequency (days)							Severity					
0	1	2	3	4	5	6	7	1	2	3	4		

Did you experience any pain, redness, swelling, or burning at injection site
(please specify)

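### Appendix E gives unblinded subjects two conflicting rules on which symptoms to rate, and one of them can bias the change in maximum DAES toward benefit

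*Combined protocol and SAP*

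**What the plan says.** The Protocol Summary states the design: "This will be an open-label pilot study". There is no control arm. Section 3.3.1 defines the primary endpoint as a fall in the number and severity of EAE symptoms after three doses, "as compared to symptoms logged in the approximately monthly cycle preceding initiation of mepolizumab". Section 15.1 turns this into the analysis variable, the maximum DAES in each cycle, but neither it nor section 15.2 says how the score is built from the log.

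Appendix E, the daily log, carries two rules:
- The instructions at the top ask for the severity of symptoms "experienced due to your EAE each day".
- The line inside the grid asks for a rating of 1 to 4 for any symptom in the list, with no condition on cause.

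The grid has eight named EAE rows (fever, aches, swelling, lymph nodes, hives, rash, fatigue, headache), a row for injection-site reactions and a free-text row for other symptoms.

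Appendix F, the weekly log, repeats the restriction: "Record symptoms you have experienced in the past week due to your EAE". Section 7.1.3 limits that log to later use: "For subjects in the de-escalation phase, after Visit 8 until study completion".

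Section 8.1.1 lists common mepolizumab reactions as "headache, injection site reactions (pain, erythema, swelling, itching, burning), back pain, and fatigue". Among the package-insert risks it lists "hypersensitivity reactions including anaphylaxis, angioedema, bronchospasm, hypotension, urticaria, and rash".

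**The concern.** The instruction at the top of Appendix E asks subjects to judge cause before they record anything, and they know when they have been dosed. Before Visit 4 the study drug cannot be the explanation. After Visit 4 it can, and subjects will have heard its risks at consent (section 16.1). A headache that belongs to the EAE cycle is rated in the baseline cycle, but may go unrated in a later cycle if the subject blames the infusion.

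The comparison would then mix a change in symptoms with a change in what is recorded. No control arm absorbs the difference. Section 15 has no rule to score symptoms regardless of cause, no adjudication and no sensitivity analysis for attribution. A blank row does not show whether the symptom was absent or was attributed elsewhere.

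Because the form carries both rules, subjects may differ in which one they follow, or may change after dosing.

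**Working it through.** **Overlap between log rows and drug risks.** Headache and fatigue are listed among reactions with at least 5% incidence. Hives (urticaria), rash and swelling (angioedema) correspond to hypersensitivity risks for which section 8.1.1 gives no frequency. So 2 of the 8 named EAE rows overlap common reactions, and 5 of 8 overlap any listed reaction or risk.

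**Inputs for the simulation (section 15.1).** n=5 and 4 cycles (1 baseline, 3 post-dose). Maximum DAES ~ Poisson(a·e·f), with a ~ gamma(mean 3, variance 3) and e ~ gamma(mean 1, variance 0.25). f = 1 at baseline and 1 − r/100 afterwards. Quasi-Poisson fit with fixed person effects, dispersion not below 1, t-distribution. The Protocol Summary gives N = 12, so both sizes were run.

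**Formulas.** With B the baseline total and S the post-dose total:
- rate ratio = (S/3)/B
- variance of log ratio = φ(1/B + 1/S), with φ = max(1, Pearson χ²/df)
- df = 4n − n − 1, which is 14 for n=5 and 35 for n=12

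**The plan's own figures reproduce (n=5).**

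| Quantity | Stated | Simulated |
|---|---|---|
| Power at 87.5% reduction | over 91% | 91.1% |
| Power to show at least 30% reduction | 80% | 80.0% |
| Two-sided type I error | 4.9% | 4.9% |
| One-sided type I error (benefit) | 3.4% | 3.5% |

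**Under-scoring with no true effect.** Let m be the share of the post-dose mean score lost to misattribution. The documents give no value, so m is an assumption. Setting f = 1 − m after dosing (40,000 data sets per row) gives the chance of a significant reduction:

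| m | n=5 | n=12 |
|---|---|---|
| 0 | 3.4% | 3.8% |
| 5% | 4.6% | 5.9% |
| 10% | 6.2% | 8.7% |
| 20% | 9.5% | 17.2% |
| 30% | 15.4% | 30.7% |
| 50% | 35.9% | 70.5% |

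**Can it mimic the planned effect?** At m = 30%, the 95% interval shows a reduction of at least 30% in only 3.2% (n=5) or 4.2% (n=12) of data sets. With a true 87.5% reduction at n=5 the figure is 80.0%.

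**What misattribution would m require?** Suppose, for illustration only, that DAES is a sum in which the eight rows weigh equally, and that a fraction q of ratings on the overlapping rows is lost.
- All five overlapping rows at risk: m = (5/8)q. Then m = 10% needs q = 0.10/0.625 = 16%, and m = 20% needs 32%.
- Headache and fatigue only: m = (2/8)q. The same losses need q = 40% and 80%.

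If DAES is instead the worst single item, losing one row often leaves the score unchanged and m would be smaller. Taking the maximum over a cycle also favours days on which less was lost.

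**The case against.** The strongest reply is that the form itself limits the problem. The grid line asks for any listed symptom, and the direction to leave rows blank applies only to symptom-free days, so no text tells a subject to omit a symptom blamed on the drug. This stands, and it makes the defect a conflict between two rules rather than one clear wrong rule. It does not remove the bias, because a subject who follows the instruction at the top can still omit such a symptom.

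A reader might infer several stronger things that the documents do not support:
- **That every symptom blamed on the drug becomes a false treatment effect.** The endpoint is EAE symptoms. Omitting a new symptom that the drug truly caused creates no false fall from baseline. Only a real EAE symptom blamed on the drug does.
- **That the bias can run only toward benefit.** The injection-site row is rated on the same 1 to 4 scale and becomes relevant only after dosing. If it counts in DAES it raises post-dose scores, as does a drug-caused headache rated under the grid rule. All three primary-phase doses are intravenous, so the row may be used little, but the plan does not exclude it.
- **That both logs distort the primary endpoint.** The weekly log is used after Visit 8 and bears only on the exploratory de-escalation endpoint.
- **That safety information is lost.** Section 12.2 elicits adverse events at every contact and records them whether related or not.
- **That nothing else could reveal the problem.** The daily Angioedema Activity Score (Appendix G) asks about any swelling episode without attributing cause. It covers swelling only and has no place in section 15, so it is a partial backstop.

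**Conclusion.** The point holds as a correctable weakness in the primary instrument. Appendix E gives conflicting rules, and under one of them the recording of true EAE symptoms can change when treatment starts. The direction toward benefit is plausible but not certain, because the injection-site row may offset it.

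The size cannot be determined from the documents. On the plan's own model, losing 10–20% of the post-dose score with no true effect would raise the false-benefit rate to about 6–10% at n=5 or 9–17% at n=12, from 3.4–3.8%. These figures rest on an assumed loss and on an undefined score. The threat is to the test against zero and to the size of the estimated reduction. A result near the planned 87.5% could not credibly be put down to attribution alone.

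**What to change.** 1. In Appendix E, replace the attribution wording with one instruction: rate every listed symptom, whatever the subject thinks caused it. Make the same change in Appendix F for the exploratory de-escalation endpoint.
2. Beside each rated symptom add a tick-box for perceived cause (EAE, study drug, other, unsure).
3. Define DAES in section 15.1 item by item. Build it from the EAE symptom rows, exclude the injection-site row, state whether the free-text row counts, and use the same rule before and after treatment.
4. Pre-specify both the all-cause and the EAE-attributed maximum DAES, one as primary and the other as a sensitivity analysis. Either can be defended as primary.

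The cost is a REDCap edit, a slightly longer daily form and one more run of the same model. The all-cause score may count true drug side effects against mepolizumab and so slightly lower the estimated reduction, which is why both scores should be reported. The change needs to come before data collection, since perceived cause cannot be recovered reliably afterwards.
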